2.1.2.2. Secondary SIV Immunogenicity Estimands

The estimands for the secondary SIV immunogenicity objectives will use the hypothetical strategy and estimate the SIV immune response when the intercurrent event would not occur. In other words, the immune response is estimated in the hypothetical setting where participants follow the study schedule and protocol requirements as directed.

Estimands for the secondary SIV immunogenicity objective have the following 5 attributes:

- **Treatment condition:** SIV administered at Visit 1 in the coadministration group vs SIV administered at Visit 1 in the sequential-administration group.
- **Population:** Older adults, as defined by the study inclusion and exclusion criteria.
- **Variables:** Strain-specific HAI titers (or H3N2-neutralizing antibody titers if interpretable H3N2-HAI titers cannot be obtained) measured before SIV vaccination and 1 month after the SIV vaccination visit, strain-specific HAI titer (or H3N2-neutralizing antibody titers if interpretable H3N2-HAI titers cannot be obtained) fold rise from before SIV vaccination to 1 month after SIV vaccination.
- **Intercurrent events:** Similar to [Section 2.1.1.2](#), all data after intercurrent events 1, 2, and 3, as well as all data at intercurrent event 4, if collected, will be excluded. Major protocol violations will be determined by clinical review (through the data handling memo).
- **Population-level summary:** The group means measured as GMTs and GMFRs for the 2 treatment groups separately.

2.1.3. Additional Estimand(s)

Additional estimands, as supplemental analyses to support the primary and secondary immunogenicity objectives, are defined. The table below lists the variables and strategies for addressing intercurrent events, which are listed in [Section 2.1.1](#) and [Section 2.1.2](#) for the immunogenicity objectives. The remaining 4 estimand attributes (treatment condition, variables, population, and population-level summary) are the same for each objective.

Objective	Intercurrent Events Handling Strategy
Primary RSV Immunogenicity	Treatment policy
Primary SIIV Immunogenicity	Treatment policy
Secondary RSV Immunogenicity	Treatment policy
Secondary SIIV Immunogenicity	Treatment policy

2.2. Study Design

This is a Phase 3, multicenter, randomized, parallel-group, double-blind, placebo-controlled study, with approximately 1400 participants to be enrolled in Australia and/or another country in the southern hemisphere.

Healthy adults ≥ 65 years of age will be randomized 1:1 to either the coadministration group (RSVpreF + SIIV)/placebo or the sequential-administration group (placebo + SIIV)/RSVpreF.

There are 3 scheduled study visits each 1 month apart. To assess immunogenicity, 30 mL blood will be collected prior to vaccination at Visit 1 (Day 1) and Visit 2 (Month 1), and at Visit 3 (Month 2).

Local reactions (redness, swelling, and pain at the injection site) occurring at the RSVpreF or placebo injection site (left deltoid) and systemic events (fever, headache, fatigue, nausea, vomiting, diarrhea, muscle pain, and joint pain) occurring within 7 days after each vaccination visit (Visit 1 and Visit 2) will be prompted for and collected daily by the participant in an e-diary device or smartphone app. SIIV injection site reactions will not be routinely collected in the e-diary.

AEs and SAEs will be collected from the signing of informed consent through Visit 3.

3. ENDPOINTS AND BASELINE VARIABLES: DEFINITIONS AND CONVENTIONS

3.1. Primary Endpoint(s)

3.1.1. Primary RSV Immunogenicity Endpoints

RSV A– and RSV B–neutralizing antibody titers will be determined on sera collected at all 3 visits. Only the RSV NTs measured at the Month 1 visit in the coadministration group and RSV NTs measured at the Month 2 visit for the sequential-administration group are relevant to the primary RSV immunogenicity endpoints.

Titers above the LLOQ are considered accurate and their quantitated values will be reported. Refer to [Section 5.3.2](#) for LLOQ details. Titers below the corresponding LLOQ, or denoted as BLQ, will be set to $0.5 \times \text{LLOQ}$ for analysis. Missing assay results will not be imputed.

3.1.2. Primary SIIV Immunogenicity Endpoints

HAI titers to the influenza strains in the SIIV administered will be determined on sera collected at Visits 1 and 2 (prior to and 1 month after SIIV administration). H3N2-neutralizing antibody titers may be determined if the H3N2 strain in the SIIV fails to hemagglutinate or hemagglutinates via neuraminidase rather than hemagglutinin, which may invalidate the HAI assay for H3N2. Only the immunogenicity measured at Visit 2 is relevant to the primary SIIV immunogenicity endpoints.

Titers below the corresponding LLOQ, or denoted as BLQ, will be set to $0.5 \times \text{LLOQ}$ for analysis. Missing assay results will not be imputed.

3.1.3. Primary Safety Endpoints

In general, e-diary data that are confirmed as errors will not be used for derivation or analysis. Below is a list of safety endpoints that will be derived.

- Local reactions within 7 days after Vaccination 1 (Visit 1).
- Local reactions within 7 days after Vaccination 2 (Visit 2).
- Systemic events within 7 days after Vaccination 1 (Visit 1).
- Systemic events within 7 days after Vaccination 2 (Visit 2).
- AEs within 1 month after Vaccination 1 (Visit 1).
- AEs within 1 month after Vaccination 2 (Visit 2).
- SAEs within 1 month after Vaccination 1 (Visit 1).
- SAEs within 1 month after Vaccination 2 (Visit 2).

3.1.3.1. Local Reactions Within 7 Days After Vaccination 1

The local reactions reported in the e-diary are redness, swelling, and pain at the injection site from Day 1 through Day 7 after Vaccination 1, where Day 1 is the day of vaccination with RSVpreF or placebo at Visit 1. This section describes derivations with details for the assessment of local reactions: any presence, maximum severity, duration, and onset day of local reactions, in addition to presence of local reactions on each day.

3.1.3.1.1. Presence of Local Reactions Within 7 Days After Vaccination 1

For the summary of the presence (yes or no) of a local reaction during the interval from Day 1 through Day 7 after Vaccination 1, where Day 1 is the day of Vaccination 1, the following 2 variables are derived for each participant included in the reactogenicity subset:

1. Presence (yes or no) of each local reaction on any day (Day 1 through Day 7).

The derivation is described in Table 3.

Table 3. Derived Variables for Each Local Reaction

Variable ^a	Yes (1)	No (0)	Missing (.)
Any day (Days 1-7)	The participant reports the reaction as “yes” on any day (Days 1-7).	The participant reports the reaction as “no” on all 7 days or as a combination of “no” and missing on all 7 days.	The participant reports the reaction as missing on all 7 days.

- a. The variable will be defined for each of the 3 local reactions.

2. Presence (yes or no) of any local reaction on any day (Day 1 through Day 7).

For any local reaction on any day, a similar definition can be applied as given in Table 4.

Table 4. Derived Variables for Any Local Reaction

Variable	Yes (1)	No (0)	Missing (.)
Any day (Days 1-7)	The participant reports any local reaction as “yes” on any day (Days 1-7).	The participant reports all reactions as “no” on all 7 days or as a combination of “no” and missing on all 7 days for all 3 local reactions.	The participant reports all local reactions as missing on all 7 days.

3.1.3.1.2. Maximum Severity of Local Reactions Within 7 Days After Vaccination

The grading of local reactions is listed in Table 5.

Table 5. Grading Scale for Local Reactions

	Mild Grade 1	Moderate Grade 2	Severe Grade 3 ^a	Grade 4 ^b
Redness	2.5 cm to 5.0 cm (5 to 10 measuring device units)	>5.0 cm to 10.0 cm (11 to 20 measuring device units)	>10 cm (>20 measuring device units)	Necrosis or exfoliative dermatitis
Swelling	2.5 cm to 5.0 cm (5 to 10 measuring device units)	>5.0 cm to 10.0 cm (11 to 20 measuring device units)	>10 cm (>20 measuring device units)	Necrosis
Pain (at the injection site)	Does not interfere with activity	Interferes with activity	Prevents daily activity	Emergency room visit or hospitalization for severe pain at the injection site

Abbreviation: e-diary = electronic diary.

- a. The maximum reaction size in measuring device units is 21 (10.5 cm). Any reaction size >21 measuring device units is recorded as a number that is >20 (eg, 21) in the e-diary.
- b. Grade 4 assessment should be made by the investigator using the AE severity grading scale. The assessment will be collected on the AE case report form and thus not reported from the e-diary.

The following variables are derived for each participant included in the reactogenicity subset:

1. Maximum severity of each local reaction on any day (Day 1 through Day 7).

The maximum severity (highest grading) of each local reaction within 7 days after vaccination will be derived. The maximum severity will be derived as follows:

- = Missing, if values are missing for all days (Days 1-7);
 - = 0, if the participant reports all reactions as “no” or a combination of missing and “no” for all days (Days 1-7);
 - = *Highest grade* (maximum severity) within 7 days after vaccination, if the answer is not “no” for at least 1 day.
2. Maximum severity of any local reaction on any day (Day 1 through Day 7).

The maximum severity for any local reaction will be derived as follows:

- = Missing, if values are missing for all days (Days 1-7) across all 3 local reactions;
- = 0, if the participant reports all reactions as “no” or a combination of missing and “no” for all days (Days 1-7) for all individual local reactions;
- = *Highest grade* (maximum severity) within 7 days after vaccination, if the answer is not “no” for at least 1 day for at least 1 local reaction.

3.1.3.1.3. Duration of Each Local Reaction

The duration of each local reaction will be calculated in days as the resolution date of reaction - start date of reaction + 1. Resolution of the event is the last day on which the event is recorded in the e-diary or the date the event ends if it is unresolved during the participant e-diary recording period (end date collected on the CRF) unless chronicity is established.

If there is no known end date, the duration will be considered unknown and set to “missing.” Participants with no reported reaction have no duration.

As there is a second vaccination at Visit 2, the date the reaction ended for Vaccination 1 should not be after the beginning of Vaccination 2. Therefore, if a reaction is ongoing at the time of Vaccination 2, the end date for the reaction after Vaccination 1 would be the date of the day before Vaccination 2, which will be used for the duration computation.

3.1.3.1.4. Onset Day of Each Local Reaction

The onset day of each local reaction will be derived. Onset day is defined as the first day of reporting any severity.

For the onset day of each local reaction, if the participants report changes in severity of the local reaction, only the first day of reporting that specific local reaction will be counted.

3.1.3.1.5. Presence of Each and Any Local Reactions on Each Day and Any Day

Presence (yes or no) of each and any local reaction on each of the 7 days (Day 1 through Day 7) follows the derivation as described in [Table 6](#).

Table 6. Derived Variables for Each and Any Local Reaction on Each Day and Any Day

Variable	Yes (1)	No (0)	Missing (.)
Each local reaction on a specific day	The participant reports the reaction on a specific day for a specific local reaction.	The participant reports the reaction as “no” on that specific day.	The participant reports the specific local reaction as missing on that specific day.
Any local reaction on a specific day	The participant reports the reaction on a specific day for any of the 3 local reactions.	The participant reports the reactions as “no” or a combination of “no” or missing on that specific day across all 3 local reactions.	The participant reports all 3 local reactions as missing on that specific day.
Each local reaction on any day	The participant reports that local reaction on any day (Days 1-7).	The participant reports the local reaction as “no” or a combination of “no” and missing across all 7 days.	The participant reports the local reaction as missing on all 7 days.
Any local reaction on any day	The participant reports any local reaction on any day (Days 1-7).	The participant reports the reactions as “no” or missing across all 7 days and across all 3 local reactions.	The participant reports all 3 local reactions as missing on all 7 days.

3.1.3.2. Local Reactions Within 7 Days After Vaccination 2

The variables to be derived for local reactions reported in the e-diary within 7 days after Vaccination 2 is similar to that after Vaccination 1.

Day 1 is the day of vaccination with RSVpreF or placebo at Visit 2.

3.1.3.3. Systemic Events

Systemic events, including fever, fatigue, headache, vomiting, nausea, diarrhea, muscle pain, and joint pain, are reported via the e-diary from Day 1 through Day 7 after Vaccination 1, where Day 1 is the day of Vaccination 1 with RSVpreF or placebo, and from Day 1 through Day 7 after Vaccination 2, where Day 1 is the day of Vaccination 2 with RSVpreF or placebo. The derivations for the systemic events as described below will be handled similarly to the way local reactions are handled for the presence for each participant, severity level, duration, onset day, and systemic event on each and any day.

1. Presence (yes or no) of each systemic event on any day (Day 1 through Day 7) after Vaccination 1.
2. Presence (yes or no) of any systemic event on any day (Day 1 through Day 7) after Vaccination 1.
3. Maximum severity of each systemic event on any day (Day 1 through Day 7) after Vaccination 1.

4. Maximum severity of any systemic event on any day (Day 1 through Day 7) after Vaccination 1.
5. Duration of each systemic event after Vaccination 1.
6. Onset day of each systemic event after Vaccination 1.
7. Presence (yes or no) of each systemic event on each and any of the 7 days after Vaccination 1.
8. Presence (yes or no) of any systemic event on each and any of the 7 days after Vaccination 1.
9. Presence (yes or no) of each systemic event on any day (Day 1 through Day 7) after Vaccination 2.
10. Presence (yes or no) of any systemic event on any day (Day 1 through Day 7) after Vaccination 2.
11. Maximum severity of each systemic event on any day (Day 1 through Day 7) after Vaccination 2.
12. Maximum severity of any systemic event on any day (Day 1 through Day 7) after Vaccination 2.
13. Duration of each systemic event after Vaccination 2.
14. Onset day of each systemic event after Vaccination 2.
15. Presence (yes or no) of each systemic event on each and any of the 7 days after Vaccination 2.
16. Presence (yes or no) of any systemic event on each and any of the 7 days after Vaccination 2.

The grading scale for systemic events is provided in [Table 7](#).

Table 7. Grading Scale for Systemic Events

	Mild Grade 1	Moderate Grade 2	Severe Grade 3	Grade 4^a
Fatigue (= tiredness in diaries)	Does not interfere with activity	Some interference with activity	Prevents daily routine activity	Emergency room visit or hospitalization for severe fatigue
Headache	Does not interfere with activity	Some interference with activity	Prevents daily routine activity	Emergency room visit or hospitalization for severe headache
Vomiting	1 to 2 times in 24 hours	>2 times in 24 hours	Requires intravenous hydration	Emergency room visit or hospitalization for severe vomiting
Nausea	Does not interfere with activity	Some interference with activity	Prevents daily routine activity	Emergency room visit or hospitalization for severe nausea
Diarrhea	2 to 3 loose stools in 24 hours	4 to 5 loose stools in 24 hours	6 or more loose stools in 24 hours	Emergency room visit or hospitalization for severe diarrhea
Muscle pain	Does not interfere with activity	Some interference with activity	Prevents daily routine activity	Emergency room visit or hospitalization for severe muscle pain
Joint pain	Does not interfere with activity	Some interference with activity	Prevents daily routine activity	Emergency room visit or hospitalization for severe joint pain

- a. Grade 4 assessment should be made by the investigator using the AE severity grading scale. The assessment will be collected on the AE case report form, thus not included in the systemic event analysis.

Fever is defined as a temperature of $\geq 100.4^{\circ}\text{F}$ ($\geq 38.0^{\circ}\text{C}$). The highest temperature for each day will be recorded in the e-diary. For reporting purposes, fever will be analyzed using the following temperature ranges:

- Mild (≥ 38.0 to 38.4°C)
- Moderate (>38.4 to 38.9°C)
- Severe (>38.9 to 40.0°C)
- Grade 4 ($>40.0^{\circ}\text{C}$)

If a participant reports a fever (or severity of fever) by accident, the correct temperature will be transcribed in a data handling memo to be included in the analysis, and the temperature that is confirmed as incorrect will not be included in the analysis.

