8.2.3.1. Local Reactions – Reactogenicity

Assessment of local reactions applies to both Visit 1 (RSV/placebo administration, left deltoid) and Visit 2 (RSV/placebo administration, left deltoid). Local reactions at the SIIV injection site (right deltoid) will not be recorded in the e-diary.

Following both Visit 1 and Visit 2 vaccinations (on Days 1 through 7, where Day 1 is the day of each vaccination), the participants will be asked to assess redness, swelling, and pain at the LEFT deltoid injection site and to record the symptoms in the e-diary or personal device, in the evening.

Redness and swelling will be measured by the participant and recorded in measuring device units (range: 1 to 21 and >21; an entry in the e-diary of 21 will denote ≥ 21) and then categorized during analysis as mild, moderate, or severe based on the grading scale in [Table 2](#). Measuring device units can be converted to centimeters according to the following scale: 1 measuring device unit = 0.5 cm. Pain at the injection site will be assessed by the participant as absent, mild, moderate, or severe according to [Table 2](#).

If a severe (Grade 3) local reaction is reported in the e-diary, a telephone call with the participant should be made to ascertain further details and determine whether a site visit is clinically indicated.

Only an investigator or a qualified designee is able to classify a participant’s local reaction as Grade 4, after clinical evaluation of the participant or documentation from another medically qualified source (eg, emergency room or hospital record) or, in the case of pain at the injection site only, contact with the participant. If a participant experiences a Grade 4 local reaction, the investigator must immediately notify the sponsor. A Grade 4 reaction will be collected as an AE on the CRF. The event will be graded using the AE intensity grading scale ([Section 10.2.3](#)).

If a local reaction persists beyond the end of the 7-day e-diary period, the participant will be requested to report that information and/or any new AEs that develop to the investigator. The investigator will enter this additional information in the participant’s source notes and CRF.

Table 2. Grading Scale for Local Reactions

	Mild Grade 1	Moderate Grade 2	Severe Grade 3	Grade 4 ^a
Redness	>2.0 cm to 5.0 cm (5 to 10 measuring device units)	>5.0 cm to 10.0 cm (11 to 20 measuring device units)	>10 cm (>20 measuring device units)	Necrosis or exfoliative dermatitis

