8.2.3.2. Systemic Events

Following both Visit 1 and Visit 2 vaccinations (Day 1 through Day 7, where Day 1 is the day of each vaccination), participants will be asked to assess fatigue, headache, nausea, vomiting, diarrhea, muscle pain, and joint pain and to record the symptoms in the e-diary that evening. The symptoms will be assessed by the participant according to [Table 3](#).

If a severe systemic event is reported in the e-diary, a telephone call with the participant should be made to ascertain further details and determine whether a site visit is clinically indicated.

Only an investigator or qualified designee is able to classify a participant’s systemic event as Grade 4, after clinical evaluation of the participant or documentation from another medically qualified source (eg, emergency room or hospital record) or contact with the participant. If a participant experiences a Grade 4 systemic event, the investigator must immediately notify the sponsor. Grade 4 reactions will be collected as an AE on the CRF and graded using the AE intensity grading scale ([Section 10.2.3](#)).

Further, if a systemic event persists beyond the end of the 7-day e-diary period, the participant will be requested to report that information and/or any new AEs that develop to the investigator. The investigator will enter this additional information in the participant’s source notes and CRF.

Table 3. Grading Scale for Systemic Events

	Mild Grade 1	Moderate Grade 2	Severe Grade 3	Grade 4^a
Fatigue (= tiredness)	Does not interfere with activity	Some interference with activity	Prevents daily routine activity	Emergency room visit or hospitalization for severe fatigue
Headache	Does not interfere with activity	Some interference with activity	Prevents daily routine activity	Emergency room visit or hospitalization for severe headache
Vomiting	1 to 2 times in 24 hours	>2 times in 24 hours	Requires intravenous hydration	Emergency room visit or hospitalization for severe vomiting
Nausea	Does not interfere with activity	Some interference with activity	Prevents daily routine activity	Emergency room visit or hospitalization for severe nausea
Diarrhea	2 to 3 loose stools in 24 hours	4 to 5 loose stools in 24 hours	6 or more loose stools in 24 hours	Emergency room visit or hospitalization for severe diarrhea
Muscle pain	Does not interfere with activity	Some interference with activity	Prevents daily routine activity	Emergency room visit or hospitalization for severe muscle pain

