8.9.4. Unscheduled Reactogenicity Visits for a Grade 3 or Suspected Grade 4 Reaction

If a **severe** local reaction ([Section 8.2.3.1](#)), **severe** systemic event ([Section 8.2.3.2](#)), or fever $\geq 39.0^{\circ}\text{C}$ ($\geq 102.1^{\circ}\text{F}$) ([Section 8.2.3.3](#)) is reported in the e-diary, a telephone contact with the participant should occur to ascertain further details and determine whether a site visit is clinically indicated. If a suspected Grade 4 local reaction, systemic event, or fever is reported in the reactogenicity e-diary, a telephone contact or site visit should occur to confirm whether the event meets the criteria for Grade 4.

A site visit or referral to a healthcare facility should be scheduled as soon as possible to assess the extent of the reaction, unless:

- The participant is unable to attend the unscheduled visit, or
- The reaction is no longer present at the time of the contact, or
- The participant recorded an incorrect value in the e-diary (confirmation of an e-diary data entry error), or
- The investigator or appropriate designee determines that an unscheduled visit is not required.

This contact will be recorded in the participant's source notes and in the CRF.

If the participant is unable to attend the unscheduled visit, or the principal investigator or authorized designee determined it was not needed, any ongoing local reactions/systemic events must be assessed at the next study visit.

The reactogenicity events should be assessed by the investigator or a medically qualified member of the site staff, such as a study physician or a study nurse, as applicable to the investigator's local practice or healthcare facility, who will:

- Measure body temperature and record any fever ([Table 4](#)).
- If present, measure the minimum and maximum diameters of redness at the **LEFT** injection site.

- If present, measure the minimum and maximum diameters of swelling at the **LEFT** injection site.
- Assess any **LEFT** injection site pain in accordance with the reactogenicity grading scale provided in [Table 2](#).
- Assess any systemic events (fatigue, headache, nausea, vomiting, diarrhea, muscle pain, or joint pain) that are present in accordance with the reactogenicity grading scale provided in [Table 3](#).
- Assess for other findings associated with the reaction and record on the AE CRF, if appropriate.
- Record AEs and SAEs as described in [Section 8.3.1](#).
- Complete the participant's source documents.

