Safety	
 • Descriptive statistics will be provided for each reactogenicity endpoint for RSVpreF and placebo at both vaccination visits. Local reactions (redness, swelling and pain at the injection site) and systemic events (fever, fatigue, headache, nausea, vomiting, diarrhea, muscle pain, and joint pain) from Day 1 through Day 7 after vaccination will be presented by severity and cumulatively across severity levels. Descriptive summary statistics will include counts and percentages of participants with the indicated endpoint (Section 9.3.1.1). • AEs and SAEs will be categorized according to MedDRA terms. All of the AEs will be descriptively summarized by vaccine group within 1 month after each vaccination. • A 3-tier approach will be used to summarize AEs. Under this approach, AEs are classified into 1 of 3 tiers: (1) Tier 1 events are prespecified events of clinical importance and are identified in a list in the product’s safety review plan; there is no Tier 1 event identified for RSVpreF at this stage; (2) Tier 2 events are those that are not Tier 1 but are considered “relatively common”; a MedDRA preferred term is defined as a Tier 2 event if there are at least 1% of participants in at least 1 vaccine group reporting the event; (3) Tier 3 events are those that are neither Tier 1 nor Tier 2 events. For both Tier 1 and Tier 2 events, the 95% CIs for the difference in the percentage of participants reporting the events between the RSVpreF group and the placebo group will be calculated using the test statistic proposed by Miettinen and Nurminen¹⁶; in addition, for Tier 1 events, the asymptotic p-values will also be presented for the difference in the percentage of participants reporting the events, based on the same test statistic and under the assumption that the test statistic is asymptotically normally distributed. For Tier 3 events, counts and percentages for each vaccine group will be provided.

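### Grade 4 systemic events other than fever, and by implication Grade 4 local reactions, are not shown as Grade 4 in the reactogenicity tables, and the AE tables do not recover that level

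*SAP*

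**What the plan says.** Protocol Tables 2 to 4 (Section 8.2.3) define four severity levels for every prompted reaction. For non-fever systemic events and injection-site pain, Grade 4 rests on healthcare use. For fatigue, for example, it is "Emergency room visit or hospitalization for severe fatigue". For redness and swelling it rests on necrosis (or exfoliative dermatitis, for redness), and for fever on a temperature above 40.0 °C. Only the investigator or a qualified designee may assign it.

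The protocol sends these reactions to the AE page. Section 8.2.3.2 says of systemic events: "Grade 4 reactions will be collected as an AE on the CRF and graded using the AE intensity grading scale". Section 8.2.3.1 says of local reactions: "The event will be graded using the AE intensity grading scale". On that scale (Section 10.2.3), Grade 4 means life-threatening.

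For the analysis, protocol Table 6 says that local reactions and systemic events "will be presented by severity and cumulatively across severity levels", and it names no level to be left out. The SAP is narrower:

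- Table 7, footnote a, on systemic events: "The assessment will be collected on the AE case report form, thus not included in the systemic event analysis".
- Table 5, footnote b, on local reactions: "The assessment will be collected on the AE case report form and thus not reported from the e-diary".
- Directly below Table 7, for fever: "For reporting purposes, fever will be analyzed using the following temperature ranges", followed by a list that includes Grade 4.
- Section 6.1.3.1, the main reactogenicity analysis: a treatment policy strategy that includes everything collected, with bars divided by maximum severity.

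**The concern.** The primary safety objective compares how RSVpreF is tolerated with SIIV and 1 month after it. The protocol's risk assessment (Section 2.3.1) names stronger local and systemic reactions as a possible effect of coadministration. The top of the severity scale is therefore of direct interest.

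Under the SAP, the maximum-severity variable for a non-fever systemic event stops at Grade 3 because of a rule, whatever the investigator confirmed. A reader of the reactogenicity tables could take the lack of Grade 4 events as a finding.

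**Working it through.** The plan states no figure on this point, so the check sets the texts side by side.

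**1. Which reactions are affected.** Footnote a expressly excludes the investigator's Grade 4 assessment of the events in Table 7: fatigue, headache, vomiting, nausea, diarrhea, muscle pain and joint pain. Fever is not in that table, and its Grade 4 range is listed for analysis. Footnote b says only that local Grade 4 does not come from the e-diary. Because the local reaction variables in SAP 3.1.3.1 are built from e-diary reports, exclusion follows by implication but is not stated. One consequence is that the composite maximum severity of any systemic event (SAP 3.1.3.3, items 4 and 12) can reach Grade 4 only through fever.

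**2. Where the event then appears in the reactogenicity tables.**

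- *Diary completed on a day with the reaction.* SAP Tables 3 and 4 count it as present, and maximum severity is the highest diary grade, so Grade 3 at most.
- *Reaction only on missing days of a partly completed diary.* SAP 5.3.1.1 treats those days as no reaction, so the event counts as absent even though the investigator's record says otherwise. This could happen in practice: the e-diary accepts entries only in a fixed daily window (protocol 8.2.3), and participants are asked to complete it between 4 PM and midnight (protocol 8.9.1). Someone in an emergency room may miss it.
- *All 7 days missing.* The participant is left out of the analysis (SAP 5.3.1.1 and 6.1.3).

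**3. Whether the AE tables recover the level.** They carry the event but do not identify it as a prompted Grade 4 reaction.

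- *Scale.* Reactogenicity Grade 4 for headache is an emergency room visit or hospitalization for severe headache; AE Grade 4 is a threat to life. Such a visit may well be graded severe on the AE page, which is AE Grade 3. Both SAP footnotes have the Grade 4 assessment made on the AE scale, while the columns they annotate use the other definition.
- *Interval.* SAP 3.1.3.4 counts AEs from vaccination to the next visit, scheduled 28 to 35 days later. Reactogenicity covers Days 1 to 7.
- *Display.* SAP 6.6.1 summarises individual AEs by MedDRA term. SAP 6.1.4.2 adds severe and life-threatening AEs. No planned table isolates prompted Grade 4 reactions.
- *Seriousness.* Hospitalization makes an event an SAE (protocol 10.2.2), but the term generally means admission. An emergency room visit without admission is reactogenicity Grade 4 and need not be an SAE.

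**4. Scale, for illustration only.** The documents give no Grade 4 rate, so the counts and rates below are assumptions. The group size is 700 (protocol 4.1). The exact (Clopper-Pearson) 95% upper limit for 0 of 700 is 1 − 0.025^(1/700) = 0.53%.

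| Assumed participants with Grade 4, of 700 | Percentage | 95% CI |
|---|---|---|
| 0 | 0% | 0 to 0.53% |
| 1 | 0.14% | 0.004 to 0.79% |
| 2 | 0.29% | 0.03 to 1.03% |
| 3 | 0.43% | 0.09 to 1.25% |

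The chance of at least one such participant in a group is 1 − (1 − p)^700. It is about 30% at p = 0.05%, 50% at p = 0.1% and 75% at p = 0.2%.

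**The case against.** The strongest reply is that nothing is hidden. AEs and SAEs are themselves primary safety endpoints with their own main analysis by vaccine group and interval (SAP 6.1.4), and every Grade 4 reaction is sent to the AE page. The routing and the re-grading come from the protocol, which the SAP follows. Presentation by severity does not explicitly promise a Grade 4 row. Safety is descriptive, so no test or primary conclusion depends on this. All of that stands, and it limits the point to how severity is displayed in the reactogenicity tables. It does not explain why fever is treated differently, how footnote a fits with including all collected data, or why one column carries two definitions of Grade 4.

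Three stronger readings are tempting, and the documents do not support them:

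- *The worst reactions are missing from the primary safety tables.* They are not, because the AE tables carry them, and the SAE tables do so where they are serious.
- *A diary entry that prompts a Grade 4 query drops out of the count.* Protocol 8.9.4 provides for this case ("If a suspected Grade 4 local reaction, systemic event, or fever is reported in the reactogenicity e-diary"). Such an entry is not a negative answer, so it counts as present under SAP 3.1.3.1, and only diary data confirmed as errors are discarded. The SAP does leave open which grade the entry receives. Complete loss arises only through missing diary days.
- *The plan would report 0 of 700 with an upper limit of 0.53%.* Under footnote a it reports no Grade 4 estimate at all for non-fever systemic events.

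**Conclusion.** The point holds for the reactogenicity tables. Grade 4 systemic events other than fever are excluded as Grade 4 by an explicit SAP rule, and Grade 4 local reactions by implication. The rule understates maximum severity for anyone affected. It conflicts with the Grade 4 columns, the fever list, the inclusion of all collected data in SAP 6.1.3.1 and the presentation by severity in protocol Table 6.

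The number of participants affected is unknown and probably small. The conclusion rests on the text and not on the illustrative counts. For local reactions it also assumes that footnote b, with variables built only from e-diary reports, means exclusion. The change is worth making because these tables address a named coadministration risk and the correction is cheap.

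**What to change.** In SAP 3.1.3.1.2 and 3.1.3.3:

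- Delete the clause after the comma in "The assessment will be collected on the AE case report form, thus not included in the systemic event analysis", and reword footnote b to match.
- Count an investigator-confirmed Grade 4 reaction (criteria of protocol Tables 2 to 4) that starts on Days 1 to 7 as present, with maximum severity Grade 4. Take it from the existing AE or unscheduled-visit CRF records.
- State that this overrides the missing-day rule in SAP 5.3.1.1. State also how a confirmed case with no diary data is handled, since SAP 6.1.3 limits the analysis to participants with some diary data.
- Show Grade 4 in the severity tables and bars by vaccine group and vaccination, and keep the AE record.
- Reconcile the footnotes' reference to the AE severity scale with the column definitions.

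No new assessment is needed, since investigators already confirm and record Grade 4. The cost is SAP wording and a merge of two sources. If the existing CRF pages do not identify a confirmed reactogenicity Grade 4, one flag would be needed. The downside is that diary and investigator reports are combined in one variable, which a table footnote should state.
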